12.4 Endpoints and Minimum Significant Differences

12.4.1 Definition of Analysis Sets

Definitions of Populations to be Analyzed:

Enrolled Population

All screened subjects who provide informed consent, regardless of the subject's randomization and treatment status in the trial.

Full Analysis (FA) Population

All subjects in the enrolled population who were randomized, received a study vaccination. This population will serve as the primary analysis population for all safety objectives. The analysis based on this population will serve as the supportive results for all immunogenicity objectives. Subjects will be analyzed as received.

Per Protocol (PP) Population

All subjects in the Full Analysis population who have valid post-vaccination immunogenicity measures with no major protocol violations that are determined to potentially interfere with the immunogenicity assessment of the study vaccine. This population will serve as the primary analysis population for all immunogenicity objectives.

The criteria for exclusion of subjects from the Per Protocol Population will be established before breaking the blind and will be based on the blinded review of protocol violations.

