All subjects in the Full Analysis population who have valid baseline (Day 1)¹ and a post-vaccination immunogenicity measure with no major protocol violations that are determined to potentially interfere with the immunogenicity assessment of the study vaccine. This population will serve as the primary analysis population for all immunogenicity objectives.

The criteria for exclusion of subjects from the Full Analysis Population and Per Protocol Population will be established by the study statistician and the study medical officer before breaking the blind and will be based on the blinded review of protocol violations.

III. MISSING DATA

In the event that missing dates or times are needed to compute durations of outcomes, the following rules will be applied:

- If the month and year are known, but the date is missing, the 15th will be used for any calculations of relative time (e.g., UNMAY2012 will become 15MAY2012).
- If only the year is known, but the month and date are missing, June 15th of the known year will be substituted for any calculations of relative time (e.g., UNUNK2011 will become 15JUN2011).
- If the minutes of start or stop times are missing, time will be assumed to be on the hour for a 24 hour clock (e.g., 11:UN, is assumed to be 11:00 AM).

If some safety data is available for the subject in safety population but respective data is missing then subject will be included in the analysis and data will be treated as follows:

1. For solicited AEs, if the severity for all 7 days are missing or the diary card was not completed or was marked as ‘unknown’ then the aggregated value will be set to missing and the subject will be excluded from the analysis. If the intensities are missing for only some of the days then the missing intensities will be evaluated as the maximum of the previous and next non-missing value for calculation of the aggregated value. For example if fever intensity is recorded as 1, (blank field), 2, 0, 0, for day 0 to day 4, then the missing day 2 intensity is imputed to be 2. Severity is missing for any AE then it will be considered as AE of maximum severity (Grade 3) “Severe” unless it’s captured as SAE. For SAE missing severity will be considered as maximum severity (Grade 4) “Life Threatening”
2. If “Relationship” is missing then it will be considered as “Related” to vaccine administered i.e. study vaccine/ placebo.

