All screened subjects who provide informed consent, regardless of the subject's randomization and treatment status in the trial.

B. Full Analysis (FA) Population

All subjects in the enrolled population who were randomized, received a study vaccination. This population will serve as the primary analysis population for all safety objectives. The immunogenicity analysis based on this population will serve as the supportive results for all immunogenicity objectives. Subjects who withdraw or are terminated from the study will be included in the FA data set until the time of withdrawal or termination. Subjects will be analyzed as received; that is, allocation errors, if any, are taken into account.

C. Per Protocol (PP) Population

All subjects in the Full Analysis population who have valid baseline (Day 1)¹ and a post-vaccination immunogenicity measure with no major protocol violations that are determined to potentially interfere

¹ The protocol does not state this requirement.

with the immunogenicity assessment of the study vaccine (e.g., missed the 2nd vaccination). This population will serve as the primary analysis population for all immunogenicity objectives.²

The criteria for exclusion of subjects from the Full Analysis Population and Per Protocol Population will be established by the study statistician and the study medical officer before breaking the blind and will be based on the blinded review of protocol violations.

III. MISSING DATA

In the event that missing visit dates or study contact dates are needed to be imputed for couples of study forms, the following rules will be applied:

- The month and year are known, but the date was missing, the 15th was used for any calculations of relative time (e.g., UNMAY2016 will become 15MAY2016).

For missing safety related data, the following rules will be applied:

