Before unblinding the study data, FHI360 statisticians will provide blinded data to the study statistician and the study medical officer to establish the criteria for exclusion of subjects from the Full Analysis Population and Per Protocol Population, and to review protocol violations. The final data analysis will initially be prepared with blinded study product group. After all analysis programs and output tables for the final analyses are verified, all analysis programs will be re-ran with the unblinded study product code given by the study randomisation statistician. In addition, the FHI360 randomisation statistician will verify with IVAC that no errors were made in study product assignment and dispensing of vaccines.

V. MULTIPLICITY CONSIDERATION

In general, since the purpose of the Phase 2 assessment is to select the dose for the Phase 3 component and the final confirmatory analysis will be solely based on the data generated for the Phase 3 component, there is no need to make an adjustment to the Type I error rate between the Phase 2 and Phase 3 components of the study.

Specifically, the analysis of immunogenicity data has a single primary endpoint and it maintains the experiment-wise Type I error rate at 2-sided of 0.05. No multiplicity adjustment to the error rate, alpha, will be made for secondary immunogenicity endpoints.

In addition, no formal hypothesis testing will be conducted for safety data analyses, therefore, no multiplicity adjustment will be performed.

VI. DESCRIPTIVE ANALYSIS

A. Study Participant Disposition

A flowchart or table showing the number screened, enrolled, randomized, vaccinated, withdrawn and its reasons, and numbers in the Full Analysis and Per Protocol Populations with protocol deviations reported on the Protocol Deviation/Violation (PDV) CRF will be produced.

B. Descriptive Statistics

Descriptive statistics will be presented in summary tables by each group, each time visit and overall. Categorical variables will be summarized by frequencies and percentages. Continuous variables will be summarized by means, standard deviations, medians, interquartile ranges, minima and maxima.

C. Baseline Data

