VIII. ANALYSIS OF SAFETY OBJECTIVES

Objective: To evaluate the safety and tolerability of two injections given 21 days apart of A/H5N1 vaccine.

Analysis Population: The Full Analysis Population will be used for the safety objective analysis.

⁴ Note that this endpoint is expected to be equivalent to another commonly used endpoint of seroconversion as defined as a post-vaccination titer $\geq 1:40$ if baseline titer $< 1:10$ OR significant increase in antibody titer post vaccination (at least a four-fold increase from baseline titer) if baseline titer is $\geq 1:10$, since all subjects are expected to have baseline titer of $< 1:10$. If at least one subject has baseline titer $\geq 1:10$, an additional endpoint of seroconversion as defined above will also be analyzed

Endpoints: The safety profile of IVACFLU-A/H5N1 will be evaluated by the number and the proportion of subjects experiencing AEs, related or not related, of the following categories for all subjects and by age group (18-40 years of age and 41-60 years age):

- **Immediate reactions** (solicited local and systemic adverse events), occurring in the first 30 minutes post vaccination on Day 1 and Day 22, as observed by study staff. The reaction will include
 - Local signs/symptoms: redness, swelling, hardness, pain, or tenderness of the injected site of upper arms;
 - Systemic signs/symptoms: headache, fever, fatigue/malaise, muscle aches, joint aches, nausea, vomiting, and chills.
- **Solicited adverse local reactions** occur over a 7-day period (Days 1-7; Days 22-28) post each vaccination, identified or observed by study staff during home visits and/or reported by parent at any time through Day 7. Specifically, the following local signs and symptoms at site of injection will be assessed and documented as solicited adverse reactions:
 - Redness
 - Swelling
 - Induration
 - Pain
 - Tenderness
- **Solicited adverse systemic reactions** occur over a 7-day period (Days 1-7; Days 22-28) post each vaccination, identified or observed by study staff during home visits and/or reported by parent at any time through Day 7. Specifically, the following systemic reactions will be assessed and documented as solicited adverse reactions:
 - Fever/body temperature (and body location of measurement)
 - Fatigue/malaise
 - Generalized muscle aches
 - Joint aches/pains
 - Chills
 - Nausea
 - Vomiting
 - Headache

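### Both SAPs provide for excluding subjects from the Full Analysis (primary safety) population after review of protocol violations, which conflicts with that population's definition and with the protocol

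*SAP*

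**What the plan says.** Protocol 12.4.1 defines the Full Analysis (FA) population as "All subjects in the enrolled population who were randomized, received a study vaccination", analysed by product received, and says "This population will serve as the primary analysis population for all safety objectives". Its exclusion sentence covers one population only: "The criteria for exclusion of subjects from the Per Protocol Population will be established before breaking the blind".

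Section II of the interim SAP and section II of the final SAP repeat the FA definition and its safety role. Both add a rule on withdrawals that keeps people in: "Subjects who withdraw or are terminated from the study will be included in the FA data set until the time of withdrawal or termination". Both then change the protocol's exclusion sentence to read "The criteria for exclusion of subjects from the Full Analysis Population and Per Protocol Population will be established", name the study's statistician and medical officer as the people who set the criteria, and say that the criteria "will be based on the blinded review of protocol violations".

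Final SAP IV repeats the point: blinded data go to those two people "to establish the criteria for exclusion of subjects from the Full Analysis Population and Per Protocol Population". Final SAP VIII names a single population for safety: "The Full Analysis Population will be used for the safety objective analysis".

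**The concern.** FA has two entry conditions, randomization and receipt of a study vaccination, and a review of protocol violations decides neither of them. A criterion drawn from such a review would therefore act on people who already belong to FA. It would take their adverse events out of the numerator and the subjects themselves out of the denominator of the primary safety tables.

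FA is also the supportive population for immunogenicity. Section VII of both SAPs runs that supportive analysis only if FA and Per Protocol differ by more than 5% in number of subjects. If the same violations reduce both populations, the difference narrows and the check may not be triggered.

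The prefaces of both SAPs undertake to describe differences from the protocol's analysis summary. The final SAP does so for the baseline-titer requirement and for the Cochran-Mantel-Haenszel test, but not for this change.

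**Working it through.** **1. The texts side by side**

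| | Protocol 12.4.1 | Interim SAP II | Final SAP II and IV |
|---|---|---|---|
| FA entry conditions | randomized and vaccinated | same | same |
| Analysed by product received | yes | yes | yes |
| Primary for safety | yes | yes | yes (also VIII) |
| Exclusion criteria from violation review | Per Protocol only | FA and Per Protocol | FA and Per Protocol, stated twice |
| Declared as a departure | not applicable | no | no |

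The protocol is consistent with itself. Each SAP conflicts with its own FA definition and with the protocol.

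**2. Whether a harmless reading fits**

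The sentence might be meant only to leave out people who were never randomized or never vaccinated. The definition already does that, with no need for criteria or a violation review. That reading gives the reference to FA no work to do; any other reading removes randomized, vaccinated subjects.

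**3. Scale for safety (illustration only)**

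The plan gives no figure for FA exclusions. Protocol 12.2 does give exact limits, so the method can be checked first. For zero events the exact two-sided 95% upper limit is 1 − 0.025^(1/n). With n = 1100 this is 0.335%, against the protocol's 0.33%.

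The input is the Phase 3 vaccine group of 500 in the final SAP preface. Assume one SAE case in that group, and assume that this subject is the one excluded.

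- Before, 1/500 = 0.20%. The upper limit p solves (1 − p)^500 + 500p(1 − p)^499 = 0.025, giving p = 1.11%. The lower limit is 0.005%.
- After, 0/499 = 0%. The upper limit is 1 − 0.025^(1/499) = 0.74%.

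The protocol text supplied gives 1,000 in this group. The same scenario there is 1/1000 (upper limit 0.56%) changing to 0/999 (0.37%).

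Loss of precision is not the issue. If 1% to 5% of the 500 were excluded (an assumption), 495 to 475 would remain and the zero-event upper limit would be 0.74% to 0.77%, against 0.735% with all 500. What matters is losing a rare event.

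**4. Scale for the 5% trigger (illustration only)**

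Assume that the rule is applied to the roughly 270 subjects in the Phase 3 immunogenicity subset, with FA as the denominator; the SAP does not specify either.

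- 14 subjects excluded from Per Protocol only: 14/270 = 5.2%, so the supportive analysis runs.
- One of those 14 also excluded from FA: FA = 269, Per Protocol = 256, and 13/269 = 4.8%, so it is not required.

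**The case against.** The best defence is that the operative FA definition is unchanged and inclusive, that no FA exclusion criterion appears anywhere, and that one sentence serves two populations while only the Per Protocol definition mentions violations. On that view this is a drafting ambiguity. It is true that no criterion is named. But the sentence makes the violation review the basis for both sets of criteria, and final SAP IV assigns the task again, so a team following the SAP literally would be setting FA exclusions.

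The safeguards are real. The review is blinded, which limits selection by arm. Reasons for exclusion must be documented. The disposition table shows numbers vaccinated beside numbers in FA, so a gap would be visible. All SAEs are to be listed. These make a silent loss unlikely, but they do not restore the subject to the rates and confidence intervals, and neither SAP says that the listings extend to subjects excluded from FA.

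A reader might infer more than the documents support:

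- **That subjects given the wrong product would be dropped.** Both SAPs analyse by product received and say that allocation errors are taken into account, so such subjects stay in.
- **That FA loses its supportive role for immunogenicity altogether.** The role is weakened, because the difference between populations narrows; it does not disappear.
- **That the safety results are biased in a known direction.** No criterion and no mechanism differing by arm is given, and the decisions are blinded.

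**Conclusion.** Wrong as written, and worth correcting, because it concerns the primary safety population of a study intended to support registration. The conflict is established from the text alone and depends on no calculation. The practical effect is a possibility only: the documents do not show that anyone was or would be excluded from FA.

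The change from 1/500 (upper limit 1.11%) to 0/499 (0.74%) rests on two assumptions, a single SAE case and that case being the one excluded. It shows what the wording permits and is not an expected effect. A reader might pool the selected dose across phases to reach 600 recipients. The final SAP concentrates on the Phase 3 cohort and combines phases only if needed, so the Phase 3 group is the proper base for the illustration. Nor do the safety conclusions rest on SAEs alone: four of the five safety categories are solicited or unsolicited adverse-event proportions, which one exclusion would barely move. The 5% example rests on the assumed subset and denominator stated with it.

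**What to change.** In final SAP II, delete the reference to the Full Analysis Population from the exclusion sentence so that it covers Per Protocol only, as in protocol 12.4.1. Make the matching deletion in final SAP IV. Make it in interim SAP II as well for consistency; the practical gain there is small, since the final SAP describes Phase 2 as already conducted.

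Add one sentence to the FA definition: no randomized subject who received at least one study vaccination is excluded from FA for protocol violations. Keep the word randomized. A rule based on injection alone would drop a condition that the protocol sets and create a new departure.

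The cost is SAP wording only. The change restores the protocol's rule and leaves sample size, power and data collection as they are.

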5.4.3 Early Termination

An enrolled/vaccinated subject may be terminated from the study for any of these reasons:

- a) Subject withdraws consent.
- b) PI or a medical monitor involved in the study decides that termination is in the best interest of the subject.
- c) PI or a medical monitor involved in the study decides that termination is necessary to protect the integrity of the study or achieve the objectives of the study.
- d) Interruption of study schedule makes the subject's data unusable according to protocol requirements.
- e) Sponsor terminates the study.
- f) Governing IRBs recommends to terminate the study

If a subject withdraws from the study for any reason prior to the planned study duration, every attempt is made to complete the following:

- a) Report of local and systemic reactogenicity and AEs are reviewed by PI (or designee).
- b) Obtain specimens for immunogenicity analysis if withdrawal occurs prior to scheduled laboratory testing.
- c) Diary Card information is reviewed with the subject in detail by site staff, if in use since the last visit.
- d) Injection site(s) examination and a targeted physical examination are performed (if indicated).

IVAC must be informed within 48 hours of all instances of the premature termination of a subject's participation in the trial.

If the subject develops a reaction to study vaccine which the investigator believes threatens the subject's well-being, the withdrawn subject must be treated or transferred to a treatment facility.

Study Termination: IVAC retains the right to temporarily suspend or prematurely discontinue this study at any time related to safety. If the study is stopped or suspended prematurely, IVAC will inform the local Principal Investigator as well as regulatory authorities about the decision and the reasons for termination or suspension. If such action is taken, all efforts must be made to ensure the safety of the subjects enrolled in the study. The Principal Investigator will assist IVAC in informing the responsible IEC and provide the reason for the suspension or termination. In case of premature study or study site closure, the monitor will conduct all activities for final monitoring visits.

6 Study Products

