2. A study clinician will review the procedures for the vaccination study with each eligible subject. For Phase 2 subjects, a vaccine study ICF (ICF B) must be completed at this time (Phase 3 subjects have already signed the study consent). Upon entry into the trial portion of the study, the subject is assigned an ID number and may proceed to undergo further procedures related to administration of study product and evaluation of vaccine safety and immunogenicity.
3. A study clinician will perform a targeted physical examination (performed only if symptoms are present).
4. Prior to administration of study product, a serum specimen will be collected from the subject's dominant arm for anti-influenza serologic assays. This includes all subjects for Phase 2 and 1 of 3 clinical sites in Phase 3.
5. The subject will be administered one injection of study product in the deltoid of the non-dominant arm. (Injection may be given in the dominant arm if subject prefers.)
6. The subject will be observed for 30 minutes after administration in case of any immediate reactions. If the subject experiences an immediate adverse reaction, he/she will be treated and the event will be recorded on the CRF. A 30-minute Reactogenicity Assessment will be completed.
7. The subject will be given a Diary Card (and thermometer and ruler) in which the subject will be asked to record any local and/or systemic reactions that might appear from Days 1 to Day 7, and record any concomitant medications. The subject will be instructed how to use the Diary Card, thermometer and ruler. All relevant explanations should be included in the Diary Card. The Diary Card will also have contact information for the investigators, should the subject have any questions. The subject will be informed that a member of the investigator's team will visit or call the subject the next day (Day 2) and then call (or visit, if needed) 5 days after the injection (Day 6) to check on the subject's completion of the Diary Card and subject's well-being.
8. The subject will be instructed that if the subject later experiences an AE requiring medical care, the subject should inform the investigator as soon as possible and seek medical care as appropriate. If the subject visits a health care provider, the subject should be sure to inform the health care provider of participation in this study and provide the health care provider with the investigator's contact information.

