- For solicited AEs, if the severity for all 7 days are missing or the diary card was not completed or was marked as ‘unknown’ then the aggregated value will be set to missing and the subject will be excluded from the analysis. If the intensities are missing for only some of the days then the missing intensities will be evaluated as the maximum of the previous and next non-missing value for calculation of the aggregated value. For example if fever intensity is recorded as 1, (blank field), 2, 0, 0, for day 0 to day 4, then the missing day 2 intensity is imputed to be 2. Severity is missing for any AE then it will be considered as AE of maximum severity (Grade 3) “Severe” unless it’s captured as SAE. For SAE missing severity will be considered as maximum severity (Grade 4) “Life Threatening”
- If “Relationship” is missing then it will be considered as “Related” to vaccine administered i.e. study vaccine/ placebo.
- If for Start date - day of event / condition is missing for any adverse event then it will be imputed as the date of last dose of study vaccine / placebo.
- If for Start date - day and month of any adverse event is missing then it will be imputed as the date of first dose of study vaccine / placebo.
- If Stop date of any adverse event is missing then it will be treated as missing.

All immunogenicity assays reported below the limit of quantification (LLOQ, e.g. <1:10) will be assigned a value by the study lab. No missing data will be imputed.

² This definition is similar to the criteria: 1) the completion of a certain pre-specified minimal exposure to the treatment regimen; 2) the availability of measurements of the primary variable(s); 3) the absence of any major protocol violations including the violation of entry criteria; that given by ICH guideline E9: statistical principles for clinical trials: International Conference on Harmonisation of Technical Requirements for Registration of Pharmaceuticals for Human Use; 1998. Available from: <http://www.ich.org/products/guidelines/efficacy/article/efficacy-guidelines.html>.

IV. UNBLIDING STUDY CODE FOR FINAL DATA ANALYSES

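### A subject with no usable diary is dropped from the 7-day solicited-reaction summary even when staff recorded a reaction

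*SAP*

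**What the plan says.** Section III of the final SAP, and the same section of the interim SAP, gives one rule for missing solicited data. It applies "if the severity for all 7 days are missing or the diary card was not completed", or when the card is marked as unknown. In each case "then the aggregated value will be set to missing and the subject will be excluded from the analysis".

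The next sentence treats partly filled cards differently: "If the intensities are missing for only some of the days then the missing intensities will be evaluated as the maximum" of the neighbouring recorded values. The same item keeps any AE that has no severity grade and counts it as Grade 3 (Grade 4 if it is an SAE).

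The interim SAP introduces these rules by saying that a subject with some safety data stays in the analysis. The final SAP has no such lead-in.

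Section VIII of the final SAP states: "The Full Analysis Population will be used for the safety objective analysis". Section VIII of both SAPs defines 7-day solicited reactions as those found by staff at home visits, those reported, or both.

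**The concern.** Not completing the card is enough by itself to trigger exclusion, and the rule does not ask whether a reaction is known from another source. The endpoint definition is not confined to the diary, but the exclusion is. A reaction that staff found, graded and entered on the CRF can therefore be removed from both numerator and denominator.

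The 7-day local and systemic reactions are two of the five safety endpoint categories, and the only ones with a planned between-group test. In Phase 2 they were also part of the safety information that could be weighed in choosing the dose. Dropping known events can only lower the reported reaction rate, which is the wrong direction for a safety analysis.

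**Working it through.** **1. Are there sources other than the diary?** Yes.
- Protocol 8.1.2 has a clinician evaluate the solicited signs and symptoms on Days 1, 8, 22, 29 and 43, in addition to the diary.
- Protocol 7.3.3 and 7.3.7 have staff take an interim history on Days 8 and 29 and enter AEs on the CRF.
- Protocol 7.4 puts findings from unscheduled visits on the CRF.
- Protocol 5.4.3 asks for a review of reactogenicity, and of the diary if in use, when a subject leaves early.
- On Days 1 and 22, "A 30-minute Reactogenicity Assessment will be completed" (protocol 7.3.1 and 7.3.5).

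**2. Does the rule also remove partly filled diaries?** No. The SAP's own example is 1, blank, 2, 0, 0. The gap becomes max(1, 2) = 2, which agrees with "then the missing day 2 intensity is imputed to be 2". I then took every seven-day pattern of grades 0 to 3 or blank with at least one day filled: 5^7 − 1 = 78,124 patterns. In none did imputation change the 7-day maximum from the maximum of the recorded days. Two assumptions are mine: that the aggregated value is the 7-day maximum, and that a gap at either end takes its one available neighbour. One filled day is therefore enough to keep the subject.

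**3. Where else could the dropped event be counted?** Protocol 9.2.1, 9.2.6 and 9.2.7, and SAP Section VIII, class a solicited sign as unsolicited only if it starts after seven days. A non-serious fever that starts on Day 2 is not an immediate reaction, not unsolicited and not an SAE. The 7-day summary is where it belongs, and the rule takes it out.

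**4. Size, as illustration only.** The documents do not give the share of reactors without a diary. I assume 1%, 5% or 10% of the arm, every one of them a reactor known to staff, which is the worst case.

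Inputs: N = 500 vaccinees (final SAP, Preface). Phase 1 rates at 15 mcg (protocol 2.1.3, Table 5) are 26/32 = 81.3% for any solicited event and 14/32 = 43.8% for systemic events. Hence R = 500 × 26/32 ≈ 406 and R = 500 × 14/32 ≈ 219. These rates are only an anchor, because the Phase 1 systemic list included cough and sore throat, which this trial does not solicit. With m reactors dropped, the reported rate is (R − m)/(N − m) in place of R/N. Intervals are Clopper-Pearson 95%.

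| Dropped m | Any solicited event | Systemic event |
|---|---|---|
| 0 | 406/500 = 81.2% (77.5–84.5) | 219/500 = 43.8% (39.4–48.3) |
| 5 (1%) | 401/495 = 81.0% (77.3–84.4) | 214/495 = 43.2% (38.8–47.7) |
| 25 (5%) | 381/475 = 80.2% (76.3–83.7) | 194/475 = 40.8% (36.4–45.4) |
| 50 (10%) | 356/450 = 79.1% (75.1–82.8) | 169/450 = 37.6% (33.1–42.2) |

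The shifts are the same with the 1,000 vaccinees in the protocol.

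Rare severe reactions move more in relative terms. Assume 5/500 = 1.00% (0.33–2.32%). Dropping two gives 3/498 = 0.60% (0.12–1.75%). Dropping all five gives 0/495 (upper limit 0.74%).

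**The case against.** The strongest defence is that the rule, read as a whole, bites rarely. Diary entry starts on the evening of Day 1, staff check the card on Day 2, and the card is reviewed with anyone who leaves early. Most subjects who react will have at least one filled day and stay in. That stands, and it rules out the broader reading that any incomplete card leads to exclusion.

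A reader might also infer that people who withdraw after a reaction disappear from the safety results. The documents do not support this. Withdrawn subjects stay in the Full Analysis set up to withdrawal. The 30-minute, unsolicited and SAE summaries do not use the diary rule. Disposition shows withdrawals with reasons, and AE listings are planned. A general MedDRA summary might also carry the event, although the SAP does not say whether solicited reactions enter it. None of these outputs restores the event to the 7-day percentages or the group comparison.

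A third inference is that the loss is informative and falls mainly on the vaccine arm. That is plausible but not shown. The Phase 1 difference (81% to 84% against 33%) is in reactions, not in missing diaries, and no Phase 1 subject discontinued because of an AE. The effect on dose selection is also thin, because the selection table uses HAI rates alone and safety is an unquantified further factor.

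For Phase 2, the interim lead-in can be read as keeping such subjects. The first rule beneath it then excludes them, so the interim text contradicts itself and settles nothing.

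Finally, it can be said that the Grade 3 default shows that staff-recorded events are meant to be kept. If so, the rule should say so. As written, an AE with no grade is kept as Grade 3, while a reaction with a known grade but no card is lost.

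**Conclusion.** The point holds in a limited form. Read literally, both SAPs remove a subject with no usable diary from the 7-day solicited summary even when staff recorded a solicited reaction in the window, and this conflicts with their own endpoint definition. Two terms also need settling: what counts as a card not completed, and whether exclusion is per symptom, per dose or from the whole analysis.

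The size is unknown. Under the worst-case assumption above, the rate falls by 0.2 to 2.1 percentage points for any solicited event and by 0.6 to 6.2 for systemic events. The larger relative effect is on rare severe reactions. This does not undermine the safety analysis as a whole, but it is a one-directional loss of known events that wording can prevent, and it should be corrected before unblinding.

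**What to change.** In both SAPs, replace the rule with the following.

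- Count any solicited reaction recorded on the CRF with onset in Days 1–7 or 22–28 at its maximum recorded grade, whatever the diary status. Sources are the diary, the Day 8 or 29 visit, an unscheduled visit, a staff contact or the exit review.
- Set the value to missing, per symptom and per dose, only when there is neither a usable diary day nor a recorded reaction. State that a card not completed means no day filled.
- Do not treat a negative 30-minute check alone as a 7-day non-event. Keep the 30-minute endpoint reported separately.
- Report the number without diary data by arm and dose.
- Add a sensitivity analysis with all vaccinated subjects as denominator.
- In the interim SAP, reconcile the lead-in with the rule. The final SAP describes Phase 2 as already conducted, so there the change matters for any rerun and for the optional pooling of the two phases.

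The cost is wording and programming, with no new data collection. Staff contacts on Days 2, 6, 23 and 27 are described as checks on the diary and well-being, so they add data only where they led to a CRF entry. A few subjects will have mixed data sources.

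There is also a slight upward tilt, because subjects without a diary enter only when a reaction was recorded. At worst, with 219 systemic reactors and 25 excluded subjects who did not react, the rate would read 219/475 = 46.1% in place of 219/500 = 43.8%. The sensitivity analysis shows that difference.
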